AE Monitoring	X	X	X	X	X	X	X	X	X	X	X	X	X	X	Record all AEs and ECIs occurring within 30 days after the last dose of study treatment and SAEs for 90 days after the end of treatment or 30 days after end of treatment if the participant initiates new anticancer treatment (whichever is earlier). Participants with an AE of Grade >1 will be followed until the resolution of the AE to Grade 0-1 or until the beginning of a new anticancer treatment, whichever occurs first. Report treatment-related SAEs regardless of when they occur.
ECOG PS	X	X	X	X	X	X	X	X	X	X	X	X	X ^f		

Trial Period:	Screening	Treatment									End of Treatment	Posttreatment Period			Notes
Treatment Cycle/Visit		1	2	3	4	5	6	7	8 ^a	9 ^a	Discon	Safety	Efficacy Follow-up	Survival Follow-up ^b	
Scheduling Window (Days)	-42 to -1 ^c		±3	±3	±3	±3	±3	±3	Repeat ±3	Repeat ±3	At time of discon	30 days post last dose (+7 days)	Every 12, 16, or 24 weeks (±7 days)	Every 12 weeks (±7 days)	Cycles 8 and 9 will be repeated up to 4 times, for a total of 17 doses of study treatment.
Future Biomedical Research/Biomarkers															
Tissue Collection for Biomarker Studies	X ^g														Submit tumor tissue from nephrectomy and/or for M1 NED participants, tumor tissue from resected metastatic lesion(s), as indicated in Section 9.7.1. Adequacy of the sample for biomarker analysis will be evaluated by a central laboratory.
Blood for Genetic Analysis ^h		X													Collect predose.
Blood for RNA Analyses		X	X			X					X		X		Collect predose at Cycles 1, 2, and 5, at treatment discontinuation (due to any reason), and during Follow-up at disease recurrence.
Blood for TCR		X	X			X					X		X		Collect predose at Cycles 1, 2, and 5, at treatment discontinuation (due to any reason), and during Follow-up at disease recurrence.

Trial Period:	Screening	Treatment									End of Treatment	Posttreatment Period			Notes
Treatment Cycle/Visit		1	2	3	4	5	6	7	8 ^a	9 ^a	Discon	Safety	Efficacy Follow-up	Survival Follow-up ^b	
Scheduling Window (Days)	-42 to -1 ^c		± 3	± 3	± 3	± 3	± 3	± 3	Repeat ±3	Repeat ±3	At time of discon	30 days post last dose (+7 days)	Every 12, 16, or 24 weeks (±7 days)	Every 12 weeks (±7 days)	Cycles 8 and 9 will be repeated up to 4 times, for a total of 17 doses of study treatment.
Blood for Plasma Biomarker Analyses		X	X			X					X		X		Collect predose at Cycles 1, 2, and 5, at treatment discontinuation (due to any reason), and during Follow-up at disease recurrence.

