Participants may receive study treatment for up to 17 cycles (approximately 1 year) or until confirmation of disease recurrence or meeting the criteria for discontinuation of study treatment as outlined in Section 8.

Participants who discontinue from treatment without documented disease recurrence should have imaging performed at the time of discontinuation if the last assessment was more than 28 days prior AND should continue with posttreatment Follow-up procedures until disease recurrence, pregnancy, the start of new anticancer treatment, death, withdrawal of consent, or study conclusion (whichever occurs first).

The End of Treatment Visit should occur at the time study treatment is discontinued for any reason (see Section 9.10.4.).

Posttreatment Follow-up Period

After the end of treatment, each participant will undergo a Safety Follow-up Visit at least 30 days (+ 7 days) after the last dose of study treatment or before the initiation of a new anticancer treatment, whichever comes first. Participants will be followed for 30 days after the last dose of study treatment for AE/ECI monitoring (SAEs will be collected up to 90 days

after the last dose of study treatment or for 30 days following cessation of treatment if the participant initiates new anticancer therapy, whichever comes first).

All participants who complete 17 cycles or discontinue from treatment for a reason other than disease recurrence will undergo radiographic imaging follow-up (Q12W during year 1, Q16W during years 2 to 4, then Q24W in years 5 and beyond) for assessment of DFS. Imaging during follow-up should continue to be scheduled from the date of randomization. QoL questionnaires will continue to be collected once per year during the follow-up period. Survival Follow-up for survival status and the initiation of subsequent anticancer treatment will be assessed Q12W.

[figure not shown]
Three efficacy interim analyses may be conducted; see Section 10.7 for details.

Specific procedures to be performed during the trial, as well as their prescribed times and associated visit windows, are outlined in the Trial SoA - Section 2. Details of each procedure are provided in Section 9 – Study Assessments and Procedures.

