ASSURE, Sunitinib Malate or Sorafenib Tosylate in Treating Patients With Kidney Cancer That Was Removed by Surgery; ATLAS, Adjuvant Axitinib Therapy of Renal Cell Cancer in High Risk Patients; BID, twice a day; ccRCC, clear cell renal cell carcinoma; DFS, disease-free survival; EVEREST, Everolimus in Treating Patients With Kidney Cancer Who Have Undergone Surgery; HR, hazard ratio; PROTECT, A Study to Evaluate Pazopanib as an Adjuvant Treatment for Localized Renal Cell Carcinoma; SORCE, Sorafenib in Treating Patients at Risk of Relapse After Undergoing Surgery to Remove Kidney Cancer; S-TRAC, A Clinical Trial Comparing Efficacy and Safety of Sunitinib Versus Placebo for the Treatment of Patients at High Risk of Recurrent Renal Cell Cancer; TNM, tumor, node, metastasis; wk, week/weeks; y, year/years.

^a duct-Bellini RCC excluded

Source: [Patel, D. N., et al 2016]

In October 2016, results from a Phase 3 randomized, placebo-controlled study of sunitinib (S-TRAC) showed a median duration of DFS that was significantly longer in the sunitinib group (6.8 years; 95% CI: 5.8) to not reached compared with the placebo group (5.6 years; 95% CI: 3.8 to 6.6), with a HR of 0.76 for independent radiologic review, at the cost of a higher rate of toxic events. There were no statistically significant differences in OS data at the reported data cutoff. Dose reductions due to AEs were more frequent in the sunitinib group than in the placebo group (34.3% vs. 2%), as were dose interruptions (46.4% vs. 13.2%) and discontinuations (28.1% vs. 5.6%). Grade 3 and 4 AEs were more frequent in the

sunitinib group (48.4% and 12.1%, respectively) than in the placebo group (15.8% and 3.6%, respectively). The incidence of SAEs in the groups was similar (21.9% for sunitinib vs. 17.1% for placebo); no deaths were attributed to toxic effects related to study treatment [Ravaud, A., et al 2016].

These recent data are encouraging, as this is the first study to show a positive DFS in this patient population; however, the treatment discontinuation rate was high and the AEs created a meaningful burden for participants. Additionally, the study did not include those at the highest risk of recurrence, M1 NED, in the investigated patient population. Globally, there is no current treatment standard in the adjuvant setting for RCC after nephrectomy.

Rationale for Stratification

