9.3 Adverse Events, Serious Adverse Events and Other Reportable Safety Events

The definitions of an adverse event (AE) or serious adverse event (SAE), as well as the method of recording, evaluating, and assessing causality of AE and SAE and the procedures for completing and transmitting AE, SAE and other reportable safety event reports can be found in Appendix 4.

Progression of the cancer under study is not considered an adverse event as described in Section 9.3.5 – Disease-Related Events and/or Disease-Related Outcomes Not Qualifying as AEs or SAEs, and Appendix 4.

AE, SAEs, and other reportable safety events will be reported by the participant (or, when appropriate, by a caregiver, surrogate, or the participant's legally authorized representative).

The investigator, who is a qualified physician, and any designees are responsible for detecting, assessing, documenting, and reporting events that meet the definition of an AE or SAE as well as other reportable safety events. Investigators remain responsible for following up AE, SAEs and other reportable safety events for outcome according to Section 9.3.3.

9.3.1 Time Period and Frequency for Collecting AE, SAE and Other Reportable Safety Event Information

All AEs, SAEs and other reportable safety events that occur after the consent form is signed but before treatment allocation/randomization must be reported by the investigator if the participant is receiving placebo run-in or other run-in treatment, if the event cause the participant to be excluded from the trial, or is the result of a protocol-specified intervention, including but not limited to washout or discontinuation of usual therapy, diet, or a procedure.

- All AEs from the time of treatment allocation/randomization through 30 days following cessation of study treatment must be reported by the investigator.
- All AEs meeting serious criteria, from the time of treatment allocation/randomization through 90 days following cessation of study treatment, or 30 days following cessation of study treatment if the participant initiates new anticancer therapy, whichever is earlier must be reported by the investigator.
- All pregnancies and exposure during breastfeeding, from the time of treatment allocation/randomization through 120 days following cessation of study treatment, or 30 days following cessation of study treatment if the participant initiates new anticancer therapy must be reported by the investigator.

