	Specific AEs, SOCs (incidence $< 10\%$ of participants in all of the treatment groups)		X
	Change from Baseline Results (lab toxicity shift)		X
Abbreviations: AE = adverse event; CI = confidence interval; SOC = system organ class.			

Frequency of AE by time period from first dose (e.g., 0-3, 3-6, 6-9, 9-12 and beyond 12 months) may also be provided. In each time interval, the denominator is the number of participants at risk for the event during the particular time period, defined as participants who are event-free up until the start of the interval.

To properly account for the potential difference in follow-up time between the study arms, which is expected to be longer in the pembrolizumab arm, AE incidence adjusted for treatment exposure analyses may be performed as appropriate.

Time to Grade 3-5 AE

In addition to the tiered approach, exploratory analysis may be performed on the time to the first Grade 3-5 AE. The time to the first Grade 3-5 AE is defined as the time from the first day of study drug to the first event of a Grade 3-5 AE. Summary statistics will be provided.

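### The optional AE-by-time-period table in the sSAP keeps participants in the denominator after their AE collection has closed, so late-interval rates are understated if it is produced as written

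*Combined protocol and SAP*

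**What the plan says.** sSAP Section 3.6.2, below its Table 3, introduces the analysis in these terms: "Frequency of AE by time period from first dose (e.g., 0-3, 3-6, 6-9, 9-12 and beyond 12 months) may also be provided". It then fixes who is counted: "the denominator is the number of participants at risk for the event during the particular time period, defined as participants who are event-free up until" each interval begins. That is the whole definition. The safety population (sSAP Section 3.5.2) is everyone randomized who received at least one dose, and no rule removes a participant when AE collection ends. Section 3.5.2 points to Section 3.6.2 for the handling of missing safety data, but Section 3.6.2 contains no such rule.

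Collection is limited in time by protocol Section 9.3.1: "All AEs from the time of treatment allocation/randomization through 30 days following cessation of study treatment must be reported by the investigator". For serious events: "All AEs meeting serious criteria, from the time of treatment allocation/randomization through 90 days following cessation of study treatment", shortened to 30 days if new anticancer therapy begins. The AE monitoring note in the Schedule of Activities gives the same windows and one exception: "Report treatment-related SAEs regardless of when they occur". Treatment is capped at 17 cycles (protocol Section 5.1) of 21 days each (protocol Section 9.1.8.1).

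**The concern.** The numerator and the denominator of each interval rate cover different people. The denominator holds everyone without a recorded event. The numerator can only come from those whose collection window is open. Someone who takes a last dose in month 2 without the event counts as at risk in the 3-6, 6-9, 9-12 and beyond-12-month rows, although a non-serious AE in that person would not be reported in any of them.

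The purpose of such a table is to show when toxicity occurs. Produced as written, part of any fall over time is the closing of collection and not a fall in risk. Protocol Section 7.2.1 says immune-related AEs may appear several months after the last dose, so risk cannot be taken as zero once collection ends. A reader could conclude from the last row that late toxicity disappears.

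**Working it through.** The documents give no interval rate, denominator or early-stopping rate to reproduce. The timeline can be derived from them; the size of the effect needs assumptions.

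**Timeline, from the protocol.** Dose 17 falls 16 × 21 = 336 days after the first dose. AE collection closes at 336 + 30 = 366 days and SAE collection at 336 + 90 = 426 days. Twelve months is 365.25 days. An on-schedule completer therefore has 366 − 365.25 = 0.75 day of non-serious AE collection beyond month 12, and 426 − 365.25 = 60.75 days of SAE collection. Dose delays lengthen both.

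**When earlier rows are affected.** Month 9 is day 273.9. AE collection has closed by then for anyone whose last dose came before day 273.9 − 30 = 243.9, about month 8. For the rows starting at months 3, 6 and 12 the corresponding last-dose times are about months 2, 5 and 11.

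**Assumptions for the size (not in the documents).** First-event hazard *h* of 1% per month, on and off treatment. Stopping independent of the event, with the same probability *p* after each cycle, so that a share *q* stops before dose 17: (1 − *p*)^16 = 1 − *q*. A participant whose last dose is number *k* has a window closing at C_k = 21(*k* − 1) + 30 days. Write π_k for the probability that *k* is the last dose, and A and B for the interval start and end.

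- True interval risk: 1 − exp(−0.03) = 2.96%.
- Denominator as written: D = Σ π_k exp(−h·min(A, C_k)). Events after closure are not recorded, so those participants stay in D.
- Recorded events: N = Σ π_k [exp(−h·min(A, C_k)) − exp(−h·min(B, C_k))].
- Rate as written: N / D.

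**One case in full: *q* = 20%, months 9-12.** Dose 12 is on day 231, so that window closes on day 261, before month 9. Dose 13 is on day 252, so that window closes on day 282, after it. The share already closed is 1 − 0.80^(12/16) = 0.154. Open and event-free: 0.846 × exp(−0.09) = 0.773. Closed with no recorded event: about 0.147. D is then about 0.920, and 0.773 / 0.920 = 84% of it is still under collection. N / D = 2.41%, and 2.41 / 2.96 = 81%.

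| Early stopping *q* | Share of denominator under AE collection at month 9 | Rate as written, 9-12 months | Ratio to true rate | Rate with open windows only |
|---|---|---|---|---|
| 10% | 92% | 2.68% | 91% | 2.91% |
| 20% | 84% | 2.41% | 81% | 2.86% |
| 30% | 76% | 2.13% | 72% | 2.81% |

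Over a wider range, 5% and 40% early stopping give ratios of 95% and 63%. With the 90-day SAE window, the 9-12 month ratios at 10%, 20% and 30% are 93%, 85% and 77%.

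**Beyond 12 months (taken as months 12-15).** The ratio for non-serious AEs is under 1% in every case. For SAEs under the 90-day window it runs from 64% at 5% stopping to 41% at 40%. Restricting the denominator does not rescue the non-serious row: completers are still open at day 365.25, so they enter the denominator with less than one day each.

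**The case against.** Several points against the concern stand.

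- The table is optional, its cut-points are examples, and it carries no interval estimate or test. It is not in sSAP Table 3.
- The next paragraph of Section 3.6.2 offers AE incidence adjusted for treatment exposure to deal with unequal follow-up. That is also optional, and it is a separate analysis that leaves the interval denominator unchanged.
- At risk may have been meant to imply under observation. The sentence defines it otherwise, and a programmer would follow the definition.
- It would be wrong to say that nothing can be recorded after closure. Drug-related SAEs stay reportable without an end date, so they are affected less. The Schedule of Activities also marks AE monitoring in the follow-up columns, although its note limits what is recorded there.

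A reader might go further and infer that the bias favours pembrolizumab, taking the discontinuation figures of the adjuvant sunitinib trial in protocol Section 5.4 (28.1% versus 5.6%) and computing 0.719 / 0.944 = 0.76. The documents do not support that, for three reasons.

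1. Those are discontinuations due to AEs, for a different drug. Someone who stops for an AE is no longer event-free for any AE or for the AE that caused stopping. Only stopping while event-free for the category in question dilutes the rate.
2. Recurrence also ends treatment (protocol Section 8.1), and the plan expects less of it on pembrolizumab. In the model of protocol Appendix 7, with cure rate 0.3 and median 45 months, λ = −ln(1 − ln 2 / 1.204) / 45 = 0.01905 per month. The cumulative hazard at month 8 is 1.204 × (1 − exp(−8 × 0.01905)) = 0.170. DFS events by then are 1 − exp(−0.170) = 15.7% on placebo and 1 − exp(−0.67 × 0.170) = 10.8% on pembrolizumab. Combined, as independent causes, with an assumed 10% versus 5% of other stopping, the shares remaining are 0.90 × 0.892 = 0.803 and 0.95 × 0.843 = 0.801, a ratio of 1.00. If the 45-month median applies only to the non-cured, as protocol Section 10.9 words it, the ratio is 0.98.
3. sSAP Section 3.6.2 itself expects longer follow-up on pembrolizumab, which would dilute placebo more.

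**Conclusion.** The concern holds as a defect in a stated rule, with modest weight. If the table is produced as written, late-interval rates are understated, and more so in whichever arm has more event-free early stopping. The documents do not settle the direction between arms, and no between-arm ratio should be quoted.

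The 9-12 month figures (about 91%, 81% and 72% of the true rate at 10%, 20% and 30% early stopping) are illustrations. They rest on a constant 1% monthly hazard that continues off treatment and on stopping unrelated to the event. The near-zero non-serious rate beyond 12 months needs no assumed discontinuation rate: it follows from 17 three-weekly doses and a 30-day window, and only dose delays soften it. The Tier 2 and Tier 3 summaries and all efficacy analyses are unaffected.

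**What to change.** In sSAP Section 3.6.2, define at risk as event-free and still within the applicable collection window at the start of the interval: 30 days after last dose for AEs; 90 days for SAEs, or 30 if new anticancer therapy starts.

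For each interval, also show events per person-time under collection, with person-time ending at the first event or at window closure. The restricted denominator removes most of the shortfall in the 9-12 month row (2.41% becomes 2.86% against 2.96% at 20% stopping). Person-time is needed for the rest, because some windows close within the interval.

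Drop the beyond-12-month interval for non-serious AEs, or restrict it to SAEs. Drug-related SAEs reported after the window are better listed separately than counted in a rate.

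The cost is a short text change, minor programming with last-dose dates that the reporting windows already require, and smaller denominators in the late intervals.

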3.6.3 Summaries of Baseline Characteristics and Demographics

The comparability of the treatment groups for each relevant characteristic will be assessed by the use of tables and/or graphs. No statistical hypothesis tests will be performed on these characteristics. The number and percentage of participants screened and randomized, and the primary reasons for screening failure and discontinuation will be displayed. Demographic variables (eg, age), baseline characteristics, primary and secondary diagnoses, and prior and concomitant therapies will be summarized by treatment either by descriptive statistics or categorical tables.

3.6.4 Patient Reported Outcomes (PRO) Analysis

This section describes the planned analyses for the key PRO endpoints. As there is no formal hypothesis testing for PRO endpoints, nominal p-values will be provided for treatment comparisons of pembrolizumab vs. placebo. No multiplicity adjustment will be performed.

3.6.4.1 PRO compliance summary

Completion and compliance of EORTC QLQ-C30, FKSI-DRS and EQ-5D by visit and by treatment will be described. Numbers and percentages of complete and missing data at each visit will be summarized. An instrument is considered complete if at least one valid score is available according to the missing item rules outlined in the scoring manual for the instrument.

Completion rate of treated participants (CR-T) at a specific time point is defined as the number of treated participants who complete at least one item over the number of treated participants in the PRO analysis population.

$$CR-T = \frac{\text{Number of treated participants who complete at least one item}}{\text{Number of treated participants in the PRO analysis population}}$$

The completion rate is expected to shrink in the later visit during study period due to the participants who discontinued early. Therefore, another measurement, compliance rate of eligible participants (CR-E) will also be employed as the support for completion rate. CR-E is defined as the number of treated participants who complete at least one item over number of eligible participants who are expected to complete the PRO assessment, not including the participants missing by design such as death, discontinuation, translation not available.

$$CR-E = \frac{\text{Number of treated participants who complete at least one item}}{\text{Number of eligible participants who are expected to complete}}$$

The reasons of non-completion and non-compliance will be provided in supplementary table:

- Completed as scheduled
- Not completed as scheduled
- Off-study: not scheduled to be completed.

In addition, reasons for non-completion as scheduled of these measures will be collected using “miss_mode” forms filled by site personnel and will be summarized in table format. The

schedule (study visits and estimated study times) and mapping of study visit to analysis visit for PRO data collection is provided in [Table 4](#).

Table 4 PRO Data Collection Schedule and Mapping of Study visit to Analysis Visit

Study Week	Week 0 (Baseline)	Week 12	Week 24 to Week 36 (Every 12 weeks)	Week 48	Week 52	Week 104 to Week 120 (Every 16 weeks)
Study Day	1	85	Week number *7+1	337	365	Week number *7+1
Day Range	<=1	[2, 126]	[Week number*7-41, week number*7+42]	[295, 351]	[352, 546]	[Week number*7-181, week number*7+182]

3.6.4.2 Mean change from baseline

The time point for the mean change from baseline is defined as the latest time point at which CR-T ≥ 60% and CR-E ≥ 80% and week 52 was selected based on blinded data review prior to the database lock for any PRO analysis.

To assess the treatment effects on the PRO score change from baseline in the global health status/QoL and its physical functioning, nausea and vomiting symptom, diarrhea symptom, FKSI-DRS, EQ-5D-5L VAS outcome a constrained longitudinal data analysis (cLDA) model proposed by Liang and Zeger [4] will be applied, with the PRO score as the response variable, and treatment by time interaction and stratification factors used for randomization (See Section 7.3.1) as covariates. The treatment difference in terms of least square (LS) mean change from baseline will be estimated from this model together with 95% CI. Model-based LS mean with 95% CI will be provided by treatment group for PRO scores at baseline and post-baseline time point.

The cLDA model assumes a common mean across treatment groups at baseline and a different mean for each treatment at each of the post-baseline time points. In this model, the response vector consists of baseline and the values observed at each post-baseline time point. Time is treated as a categorical variable so that no restriction is imposed on the trajectory of the means over time. The cLDA model is specified as follows:

$$E(Y_{ijt}) = \gamma_0 + \gamma_{jt}I(t > 0) + \beta X_i, j = 1,2; t = 0,1,2,3, \dots k$$

where Y_{ijt} is the PRO score for participant i , with treatment assignment j at visit t ; γ_0 is the baseline mean for all treatment groups, γ_{jt} is the mean change from baseline for treatment group j at time t ; X_i is the stratification factor (binary) vector for this participant, and β is the coefficient vector for stratification factors. An unstructured covariance matrix will be used to model the correlation among repeated measurements. If the unstructured covariance model fails to converge with the default algorithm, then Fisher scoring algorithm or other appropriate methods can be used to provide initial values of the covariance parameters. In the rare event that none of the above methods yield convergence, a structured covariance such as Toeplitz

can be used to model the correlation among repeated measurements. In this case, the asymptotically unbiased sandwich variance estimator will be used. The cLDA model implicitly treats missing data as missing at random (MAR).

Line plots for the empirical mean change from baseline in EORTC QLQ-C30 global health status/QoL, its physical functioning and FKSI-DRS will be provided across time points till Week 52 as a supportive analysis.

In addition, the model-based LS mean change from baseline to the specified post-baseline time point together with 95% CI will be plotted in bar charts for EORTC QLQ-C30 global health status/QoL and its each functioning scale, symptom scale and FKSI-DRS score.

